3-Methylhistidine concentrations will be quantified by negative chemical ionization gas chromatography mass spectrometry as described in our previous studies^{52,53}. Urinary creatinine concentrations will be measured by a commercial kit. The average of three measurements on the three consecutive days at each time point will be used for statistical analysis to minimize possible day-to-day variations.

STATISTICAL ENDPOINTS AND APPROACH TO DATA ANALYSIS

This two-arm balanced double blind parallel Randomized Clinical Trial (RCT) study will be performed using an intention to treat (ITT) analysis population that includes all randomized patients.

Primary endpoint: The primary endpoint will be the count of the following events. This count will be used to create a composite score ranging from 0 to 6 by assigning 1 to each event regardless of stage, scores and severity that individual subjects encounter from 72 hours after burn injury through 12 weeks or until death or discharge, whichever occurs first:

1. Acute Kidney Injury (AKI) (KDIGO Stages 1 – 3)
2. ARDS (The Berlin ARDS Definition: Mild, Moderate, Severe)
3. Cardiovascular Dysfunction (SOFA Scores 1 – 4)
4. Coagulopathy (SOFA Scores 1 – 4)
5. Liver dysfunction (SOFA Scores 1 – 4)
6. Death (all causes)

We will calculate mean values of the composite sum scores among the study patients in the CoQ10 and placebo arms, and then test their difference by using an independent samples *t*-test if the observed data are evident to follow a normal distribution by Shapiro-Wilk's test. Otherwise, Mann-Whitney U test will be applied and the group specific medians and quartiles will be used as the summary statistics.

AKI: AKI represents the acute loss of kidney function and is associated with a profound and severe increase in morbidity and mortality in burn patients⁵⁴. Early AKI, which occurs less than 3 days post-burn, is usually related to inadequate fluid replacement during the initial resuscitation. AKI can occur later in the hospitalization and late AKI is multifactorial in origin and often associated with sepsis development⁵⁵. For the purposes of this study, we will follow the definitions and classification guidelines set forth in "AKI of Kidney Disease: Improving Global Outcomes (KDIGO)"^{56,57} (**Table 3**). Published in 2012, this guideline has been used in critically ill patients and in combat-injured populations⁵⁸.

Stage	Table 3. AKI (KDIGO)

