Data Analysis: For between-arm comparisons of single valued (either measured at once or as an aggregated variable such as AUC over a period) outcomes, we will apply chi-square test if the outcome is binary, and *t*-test or Mann-Whitney *U*-test to continuous outcomes based on the best fit of Shapiro-Wilk's test. The between-arm difference in the distributions of times to the first event and multiple events (of the six constituents) will be examined by using single event time Cox's model and the times to correlated multiple events using Cox's model allowing multivariate frailty, respectively. The incidence rates of each individual event, with- and without differentiating its severity, as a binary outcome will be compared between the two arms by means of longitudinal logistic modeling with generalized estimating equation (GEE)⁸⁴ to allow more than one events per patient. For the repeated measures analysis of the longitudinal plasma mitochondrial DNA and urine 3- methylhistidine (3-MH), we will examine if the mean levels over time are different between the two arms by using longitudinal general linear mixed effects model⁸⁵ which will provide the within group time dependency patterns as a linear effect or more complex form of non-linear patterns which would be able to characterize the time dependent treatment effects over time along with testing for time \times group interaction(s) of those model parameter(s). Total and organ-specific SOFA scores over time will also be examined by this mixed effects models of which the

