particular interest is to test if the improvement in the longitudinal mean SOFA scores is greater during certain time window. All analyses will also be extended to adjust for the influencing effects of any baseline demographic and/or clinical indications. Missing data may be unavoidable. Because the informed consent from many study enrollees will be obtained through the family members (i.e., surrogates), a small portion (up to 2% attrition rate) of the enrolled patients may voluntarily withdraw from the study. Before final analysis, we will check the missing data pattern of the outcomes first. If there are systematic differences in missing data patterns between the study groups and/or patient characteristics (e.g., burn type), we will take into account such problems in the analysis. The longitudinal mixed effects modeling will provide unbiased and consistent estimates of the effects provided that the missing data mechanism is ‘missing at random’ (MAR). If necessary, multiple-imputation will be applied to all endpoints analyses. All statistical tests will be two-sided and will adopt a 5% significance level.

Sample size calculation: The sample size of 290 study patients for this study is determined to achieve an adequate statistical power at a 5% Type-1 error rate for the primary endpoint analysis by the following statistical calculations. We first estimated the expected means and variances of the composite scores (assuming the six individual events are independent) for the Control and CoQ10 treatment arms under the assumption depicted in **Table 6** via 1000 repeated simulated data sets ($n = 5000$ each), instead of calculating them algebraically.

Each simulation run calculated the means and variances of the two arms, and the resulting average means (and variances) over 1000 simulations were 2.43 (1.04) in the placebo arm and 1.94 (1.05) in CoQ10 arm respectively. Based on the assumption about the event incidence rates and the estimated means and variances of the composite scores from the simulated data sets, the calculated required sample size per treatment arm (using PASS¹¹⁰) to detect such a difference (i.e., 20% reduction in the overall events) with 80% power at a 5% Type-1 error rate using 2-sided independent samples t-test was 142 per arm.

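### The Shapiro-Wilk condition in effect rules out the t-test that sized the trial, and the fallback has no named effect measure or confidence interval for the primary endpoint

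*Combined protocol and SAP*

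**What the plan says.** The Primary endpoint section defines a "composite score ranging from 0 to 6 by assigning 1 to each event regardless of stage, scores and severity". It opens the analysis with "We will calculate mean values of the composite sum scores among the study patients" in each arm. The t-test on the difference is then allowed only "if the observed data are evident to follow a normal distribution by Shapiro-Wilk's test". The next sentence reads: "Otherwise, Mann-Whitney U test will be applied and the group specific medians and quartiles will be used as the summary statistics".

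The Data Analysis section repeats the idea for other outcomes, applying a t-test or Mann-Whitney "to continuous outcomes based on the best fit of Shapiro-Wilk's test".

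The Sample size calculation section works only with means. It gives simulated means and variances of "2.43 (1.04) in the placebo arm and 1.94 (1.05) in CoQ10 arm respectively", describes the target as a 20% reduction in overall events, and reports that the required size "using 2-sided independent samples t-test was 142 per arm".

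None of these sections names a between-arm effect measure for the Mann-Whitney branch, or a confidence interval for the primary comparison under either branch.

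**The concern.** A score with at most seven values cannot be normal, and at this sample size Shapiro-Wilk can be expected to detect that. If it always does, the rule is no real choice between two tests: it always leads to Mann-Whitney. The trial would then be designed around one quantity, the mean number of events, and analysed through another, a rank comparison summarised by medians and quartiles. On a 0–6 scale those summaries move in whole steps, while the planned effect is about half a step. The trial could report a significant p-value beside two identical medians, with no prespecified estimate of the 20% reduction and no statement of its precision. An estimate chosen after unblinding would be open to selection.

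**Working it through.** **Inputs.** Event rates come from Table 6. The 290 patients in two balanced arms give 145 per arm. All tests are two-sided at 5% (Data Analysis); no separate level is given for Shapiro-Wilk, so 5% is used. The Sample size calculation section assumes independent events. Non-zero correlations below are this review's assumption, imposed through a latent Gaussian variable.

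**1. The sizing quantity.**
- Control mean: 0.40 + 0.40 + 0.70 + 0.70 + 0.10 + 0.08 = 2.380.
- CoQ10 mean: 0.32 + 0.32 + 0.56 + 0.56 + 0.08 + 0.064 = 1.904.
- Difference: 0.476, and 0.476 / 2.380 = 20%.
- Variances, Σp(1−p): 1.0636 and 1.0615.

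The plan's means of 2.43 and 1.94 (difference 0.49) are close but not equal to these sums. Its 142 per arm is not reproduced: 2 × (1.960 + 0.842)² × 1.045 / 0.49² = 68.3, so 69 per arm (70 with the noncentral t). That discrepancy is a separate matter. What counts here is that the trial was sized on a difference in means.

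**2. The Shapiro-Wilk condition.** In 3000 simulated trials at each of three correlations (0, 0.2, 0.4), with the full Table 6 effect, Shapiro-Wilk rejected in all of them. This held whether it was applied per arm, to the pooled data or to residuals (the plan does not say which). The largest p-value was 0.0004. With no exception in 3000 trials, the 95% upper bound on the chance of reaching the t-test is about 3/3000 = 0.1% per scenario. Further runs at 142 and 71 per arm, under no treatment effect, and at correlations 0.3 and 0.6 also gave 100% rejection.

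**3. What medians and quartiles can show.** Cumulative probabilities are exact at correlation 0.

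| Correlation | Arm | P(X≤1) | P(X≤2) | P(X≤3) | Median [quartiles] |
|---|---|---|---|---|---|
| 0 | Control | 0.193 | 0.550 | 0.866 | 2 [2–3] |
| 0 | CoQ10 | 0.358 | 0.727 | 0.940 | 2 [1–3] |
| 0.2 | Control | 0.252 | 0.544 | 0.810 | 2 [1–3] |
| 0.2 | CoQ10 | 0.405 | 0.693 | 0.890 | 2 [1–3] |
| 0.4 | Control | 0.296 | 0.541 | 0.768 | 2 [1–3] |
| 0.4 | CoQ10 | 0.440 | 0.672 | 0.848 | 2 [1–3] |

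The true medians are equal throughout. Under independence only the lower quartile differs; at 0.2 and 0.4 nothing does.

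**4. Simulated trials** (145 per arm, 3000 per column, Monte Carlo standard error at most 0.9 points).

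| | Corr. 0 | Corr. 0.2 | Corr. 0.4 |
|---|---|---|---|
| Sample medians equal | 88% | 85% | 78% |
| Median and both quartiles equal | 3% | 44% | 54% |
| Same, among trials with Mann-Whitney p<0.05 | 2% | 39% | 45% |
| Power, Welch t | 97.2% | 89.7% | 80.0% |
| Power, Mann-Whitney | 96.9% | 90.0% | 81.1% |
| Tests disagree | 0.8% | 2.3% | 3.3% |
| Mean half-width of Welch 95% CI | 0.24 | 0.29 | 0.34 |

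The share with all three summaries equal does not rise steadily with correlation: it was 61% at 0.3 and 15% at 0.6.

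**5. Is the mean difference safe without normality?** The Welch interval covered the true difference in 94.7–95.0% of trials. Welch type I error, from 20,000 null trials per scenario, was 0.049, 0.052 and 0.048. As a check on the half-width at correlation 0: 1.96 × √((1.0636 + 1.0615)/145) = 0.24.

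**The case against.** The strongest reply is that no inference is damaged. The two tests nearly always agree, type I error holds and power barely moves. Because the condition always resolves the same way, the usual complaint about a data-driven choice of test has no practical force. All of that stands, and it limits the weight of the point.

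Second, the plan computes mean scores without condition, so the observed difference will be available. This is a fair reading, but the fallback sentence then makes medians and quartiles the summary statistics, and no interval for the mean difference is planned on either reading.

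Third, other planned analyses describe the effect: component incidences, Cox models for first and multiple events, and covariate-adjusted extensions. The component differences do sum to the mean difference. None of these analyses, however, is named as the primary effect measure or gives an interval for that sum.

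Fourth, identical true quartiles arise only under correlations the documents do not give. That is correct. Under the protocol's own independence assumption the case rests on the equal medians and on the absence of any effect size, which is enough.

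Fifth, one could keep Mann-Whitney and name an effect measure for it, such as the probability that a patient in one arm scores lower than a patient in the other. That would close the reporting gap and is defensible for a bounded score, but it would still not estimate the quantity that sized the trial. The Hodges-Lehmann shift, which the plan does not propose, would not serve: in 1000 trials per scenario it was 0 in 53%, 49% and 46%, and 1 in the rest, against a true mean difference of 0.476.

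**Conclusion.** The concern holds. Under Table 6 the Shapiro-Wilk rule sends the primary analysis to Mann-Whitney in every simulated trial. The t-test that sized the trial is not run, and the plan prespecifies no estimate of the 20% reduction (0.476 events) with a confidence interval. The prescribed medians are equal in 78–88% of trials at correlations 0 to 0.4 when the planned effect is real. The harm is to the primary estimate and its match with the sizing basis, not to error control: power differs by about 1 point or less over that range. The plan should be changed on this point, but it does not threaten the validity of the test.

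The conclusion rests on the Table 6 rates and, for the correlated scenarios, on assumed latent correlations. The 100% rejection is a simulation result for these distributions, not a proof for every integer score.

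**What to change.** In the Primary endpoint section, delete the Shapiro-Wilk condition. State that the primary analysis is the between-arm difference in mean composite count with a two-sided 95% confidence interval, from Welch's t-test or a linear model with robust variance. Report the mean and the number and percentage of patients at each score from 0 to 6 by arm. Keep Mann-Whitney as a named sensitivity analysis. Add a clause to the Data Analysis section saying that its Shapiro-Wilk rule does not govern the primary endpoint.

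The text is short and needs no new data, but it changes the stated primary test, so it belongs in a protocol amendment made before unblinding. The power cost is small: Welch was 0.3 points higher than Mann-Whitney under independence and 1.1 points lower at correlation 0.4 (80.0% against 81.1%). At a correlation of 0.6, outside the main range examined, the t-test was 3.9 points lower (68.9% against 72.8%).

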In compliance with the guidelines, the following categories of surrogates (listed in preferred order) may provide consent in writing on behalf of potential subjects incapable of providing informed consent: i) court appointed guardian with specific authority to consent to participation in research or authority to make health care decisions for a class of diagnostic and therapeutic decisions inclusive of the proposed research; ii) health care proxy/person with durable power of attorney with specific authority for making health care decisions inclusive of the proposed research; or iii) spouse, adult child, or other close family member who knows the subject well and has been involved in their care. Assent of subjects will be a requirement for participation in the research unless the subject is incapable of giving assent due to his/her medical condition. A licensed physician colleague or a well-trained study investigator will obtain informed consent. Participants will be given as much time as necessary to consider participation or to discuss the study with anyone before making a decision. Routine care will be provided to the patient regardless of enrollment to the study. This fact will be explained to the patients and/or legal guardian.

Randomization procedure: Permuted-block randomization stratified by study site and Revised Baux score will be performed. This study procedure will utilize the RS2 system that was developed by the ABA's Data Coordinating Center (DCC) based out of UC-Davis and which has been used in previous burn trials successfully.

Study population:

Table 2.	
----------	--

Inclusion Criteria	Rationale
Age 18 years and older	Military age subjects. There are no limitations on gender, race, or ethnicity.
Burn patients with 20% or greater of total body surface area (TBSA) burn and equal to or less than 70% TBSA burn	Burns greater than 20% are considered to be severe and potentially life threatening. Burns larger than 70% carry an excessive mortality and confound the primary endpoint of MODS
Capable of receiving routine oral, enteral nutrition, or a combination of routine oral and enteral nutrition	CoQ10 is not available in injectable form for humans. The enrolled patients will receive tablets (softgels) or liquid form of CoQ10 or placebo.
Enrolled within 72 hours after burn injury	This timepoint is early enough that a preventative effect of CoQ10 replacement can manifest

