Patient or legally authorized representative (LAR) who is capable of giving full informed consent	Principle of autonomy
Anticipated hospital stay: 2 weeks or more	This duration is the common timeframe for MODS development should it occur.
Exclusion Criteria	Rationale
Patients with liver disease (bilirubin greater than 3 or diagnosis of liver cirrhosis) at the time of admission, hyperthyroidism that currently requires treatment, diagnosis of chronic heart failure, chronic renal failure requiring hemodialysis, malignancy currently undergoing treatment, or history of cancer or hematological malignancy treatment within 5 years	The primary endpoint of MODS scoring is intended for acute organ dysfunction. Subjects with chronic, pre-existing organ dysfunction are confounders
History of HIV or AIDS	MODS is driven by the immune system so pre-existing immune dysfunction is a confounder
Presence of concurrent injuries apart from burn injury that may produce long-term disabilities (e.g., spinal cord injury, anoxic brain injury)	Nonthermal injury is a MODS risk by itself and therefore methodologically problematic

Participation in another research study that may confound the results of this study in the opinion of the site principal investigator	Concurrent enrollments in prospective studies with non-competing endpoints are common events in academic burn centers
Pregnant women	Vulnerable population
Prisoners	Vulnerable population

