Scientific rationale for the observation period: Studies in trauma patients have suggested the organ dysfunction that develops soon after trauma (i.e., during the first 48 -72 h) rapidly resolves in a high proportion of patients and may reflect the reversible derangement of organ function induced by the inciting event or incomplete resuscitation. Thus, it has been proposed that later assessment of organ function (i.e., 3 days after injury) will yield a more accurate definition of multiple organ failure in trauma patients, which is needed to evaluate the relationship between trauma-induced organ dysfunction and prognosis^{71,72}. In the acute phase, particularly the first 72 hours after severe burn injury, organ dysfunction frequently occurs, causing AKI (e.g., oliguria), cardiovascular dysfunction (e.g., hypotension), and coagulopathy (e.g., thrombocytopenia)⁷³. In some cases, the organ dysfunction is transient and the patient may recover during the late-acute or sub-acute phase. In such cases, the recovery from organ dysfunction is associated with relatively good prognosis. In contrast, if the organ dysfunction continues beyond the acute phase or if it occurs or recurs at a later time, the clinical outcome is typically worse. Therefore, we will evaluate the effects of

CoQ10 supplementation on the aforementioned multi-organ dysfunction that patients encounter beginning 72 hours post-burn injury and thereafter.

Secondary endpoints: Secondary endpoints will be the following outcome events observed from 72 hours after burn injury through 12 weeks or until death or discharge (whichever occurs first) and the biochemical measurements in plasma and urine.

1. The six individual binary outcome MODS events and their times of occurrences, (i.e., the constituents of the primary composite score)
2. Weighted composite score of the six constituents
3. Maximum total SOFA score
4. Maximum SOFA score for each organ
5. AUC of total SOFA score (score x days)
6. AUC of SOFA score for each organ (score x days)
7. Delirium (CAM-ICU) (number of days)
8. Length of hospital stay (number of days)
9. Sepsis (Sepsis-3) (number of incidence)
10. Septic Shock (Sepsis-3) (number of incidence)
11. Plasma mitochondrial DNA (4 blood collections)
12. 3-Methylhistidine (3-MH) and creatinine in urine (a biomarker of muscle wasting)

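### The primary test uses neither pre-dose organ status nor the Revised Baux stratum, although dysfunction that began before the first dose can score; a prespecified adjustment would recover part of the power this may cost

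*Combined protocol and SAP*

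**What the plan says.** **Scoring.** Under Primary endpoint, each of five organ dysfunctions and death adds one point at any severity, from 72 hours after injury until 12 weeks, death or discharge. Nothing requires new onset. Under Scientific rationale for the observation period, the plan calls early dysfunction frequent and often transient, and gives this reason for looking later: "if the organ dysfunction continues beyond the acute phase or if it occurs or recurs at a later time, the clinical outcome is typically worse".

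**Start of treatment.** The Brief study overview has the first dose given by 72 hours. Table 2 explains the enrolment limit: "This timepoint is early enough that a preventative effect of CoQ10 replacement can manifest".

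**Eligibility.** Table 2 excludes chronic organ disease and "Patients with liver disease (bilirubin greater than 3 or diagnosis of liver cirrhosis) at the time of admission". It does not exclude acute dysfunction at enrolment. In Table 5 the liver criterion starts at a bilirubin of 1.2 mg/dl.

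**Primary comparison.** "We will calculate mean values of the composite sum scores among the study patients in the CoQ10 and placebo arms"; the difference is then tested by t-test, or by Mann-Whitney if Shapiro-Wilk does not support normality. No covariate enters, although randomization is stratified by site and Revised Baux score.

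**Adjustment elsewhere.** Data Analysis says: "All analyses will also be extended to adjust for the influencing effects of any baseline demographic and/or clinical indications". It names no covariate and no primary adjusted model, and does not mention pre-dose organ status.

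**The concern.** Dysfunction that is present at the first dose and lasts into the event window adds a point whichever arm the patient is in. To the extent that treatment does not clear it, that point carries no treatment effect, and the mean difference shrinks. Table 6 makes no allowance for this: it applies a 20% relative reduction to every component, without separating events already present from new ones.

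The three problems that the plan names as frequent in the first 72 hours (kidney injury, cardiovascular dysfunction, coagulopathy) have control rates of 40%, 70% and 70%. They supply 1.80 of the expected 2.38 points. A patient's organ status before treatment is therefore likely to predict the score, and the primary test leaves that information unused. Adjusted analyses are promised without named covariates, so the choice of model stays open until the data are in.

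**Working it through.** **1. The plan's own figure.** The stated means and variances "were 2.43 (1.04) in the placebo arm and 1.94 (1.05) in CoQ10 arm respectively", so the difference is 0.49 and the average variance 1.045. For a two-sided 5% test with 80% power:

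n per arm = 2 × (1.960 + 0.842)² × 1.045 / 0.49² = 16.40 / 0.2401 = 68.3, so 69 (70 with the exact t distribution).

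The plan states that the number "with 80% power at a 5% Type-1 error rate using 2-sided independent samples t-test was 142 per arm". That does not reproduce: 142 per arm gives about 98% power on these inputs. This is a separate matter, but it means that the plan starts with a margin if its inputs hold.

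**2. Inputs for the check.** Table 6 control rates: the five organ rates sum to 2.30 and their squares to 1.31; death is 0.08. The score mean is 2.38, and the full difference 0.2 × 2.38 = 0.476. Two assumptions are not in the documents: a share f of each organ's control events is already present at the first dose and persists, and treatment leaves those events unchanged while reducing all others by 20%.

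**3. Diluted difference.** Δ(f) = 0.20 × [(1 − f) × 2.30 + 0.08].
- f = 10%: 0.430
- f = 30%: 0.338
- f = 50%: 0.246

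Adjustment does not change these values.

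**4. Residual variance, independent events (the plan's assumption), f = 30%, all pre-dose dysfunction persisting.**
- Variance of the score: control 1.064, CoQ10 1.069, average 1.066.
- Variance of the baseline count: 0.3 × 2.30 − 0.09 × 1.31 = 0.572.
- Covariance with the score: control 0.3 × (2.30 − 1.31) = 0.297; CoQ10 0.3 × (2.30 − 0.86 × 1.31) = 0.352; average 0.3245.
- Adjusted variance: 1.066 − 0.3245² / 0.572 = 0.882.

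Power = Φ(Δ / √(2V/142) − 1.96).
- Unadjusted: 0.338 / 0.1225 − 1.96 = 0.80, about 79%.
- Adjusted: 0.338 / 0.1115 − 1.96 = 1.07, about 86%.

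**5. Transient dysfunction.** The proposed covariate would also count dysfunction that clears before 72 hours, which makes it noisier. I simulated 400,000 patients per arm, with transient positives unrelated to later events, so that only 40% of pre-dose positives persist.

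| f | Δ | Unadjusted power | Adjusted, all persist | Adjusted, 40% persist |
|---|---|---|---|---|
| 10% | 0.430 | 94% | 95% | 94% |
| 30% | 0.338 | 79% | 86% | 81% |
| 50% | 0.246 | 52% | 68% | 55% |

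The gains are at most about 1 point, 2 to 7 points, and 3 to 16 points.

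**6. Correlated events.** With a latent correlation of 0.35 (assumed) and f = 30%, unadjusted power is about 51% to 56%. If the prevalent events are a random share of the scored events, adjustment adds about 4 points (40% persist) to 13 points (all persist). If pre-dose dysfunction itself clusters in the sickest patients, the gain is about 7 to 23 points.

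The gain from the Revised Baux stratum is not included, because the documents give no figure for its relation to the score.

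**The case against.** The dilution rests on assumptions. The documents do not give the prevalent share, and the observation-period rationale says that early dysfunction often resolves quickly; the 72-hour start is there to remove it. Nor do they present CoQ10 as purely preventive: the primary objective speaks of mitigating MODS, and the rationale for the clinical secondary endpoints foresees benefit in recovery. Patients dosed well before 72 hours might improve before the window opens. The unadjusted randomized comparison is unbiased and controls the Type 1 error, and the plan does promise adjusted analyses. All of this stands. It limits the size of the point but does not remove it, because the covariate is cheap and helped in every scenario with prevalent dysfunction.

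A reader might infer four stronger things that the documents do not support:
- **That adjustment restores the lost power.** At 30% prevalent with independent events, about 7 of the 19 lost points return at best.
- **That the trial is underpowered for this reason.** On the plan's independence assumption, power stays near the 80% target up to about 30% prevalent. Larger shortfalls need a higher share or correlated events, and the documents give figures for neither.
- **That an admission bilirubin of 1.2 to 3.0 is already an event.** It scores only if the criterion is met from 72 hours on, and liver has an assumed rate of just 10%.
- **That counting persisting dysfunction is a mistake.** The rationale argues for it.

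**Conclusion.** The point holds as a missed efficiency and a gap in prespecification. The primary test omits the pre-dose organ count and a stratification factor, and the promised adjustment is unspecified. The benefit of adjusting is a range: from under 1 point to about 16 points of power at 142 per arm with independent events and 10% to 50% prevalent, and more with correlated events. The figures assume Table 6 control rates, no effect on dysfunction already present, a 20% reduction in the rest, and transient positives unrelated to later events. Any effect of treatment on existing dysfunction makes the dilution smaller. The validity of the planned test is not in question.

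**What to change.** - Record, from the last values before the first dose, how many of the five organ criteria each patient meets, with a stated rule for criteria that were not measured.
- Make the primary analysis a prespecified linear model (ANCOVA) of the 0–6 score on arm, that count and the Revised Baux stratum, with robust standard errors. This replaces the choice between t-test and Mann-Whitney by Shapiro-Wilk, and estimates a difference in means, the quantity on which the sample size is based.
- Keep the unadjusted comparison as a sensitivity analysis.
- Keep the endpoint definition, and say in it that persisting dysfunction counts.
- Add a supplementary analysis of events not present at baseline.

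These choices should be fixed before unblinding. The cost is SAP wording, one derived variable from routine data (creatinine, PaO2/FiO2, arterial pressure or vasopressors, platelets, bilirubin), and possibly a small data-entry item if the case report form does not already hold those values.
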